## **The effects of a motor imagery exercise program on tongue strength.**

**PI: [name], CCC-SLP**

**Protocol#00033331**

**Version #3; 09/04/2018**

### **1. Rationale for the study, area of current scientific concern and why the research is needed**

Although motor imagery (MI) has not yet been researched in the field of swallowing rehabilitation, the potential benefit is far reaching. Difficulty swallowing, or dysphagia, can occur in people who have a history of stroke, head injury, neurological disease (such as Parkinson's disease, ALS, etc.), and head/neck cancer. A person with dysphagia may have difficulty eating everyday foods and may require an altered diet, such as tube feedings or pureed foods. Because of this, having dysphagia is often associated with increased feelings of isolation and depression. Speech-language pathologists work with people with dysphagia to rehabilitate their swallow, with the goal of reducing their risk of choking and improving their ability to eat normal foods. The use of MI as a way to augment dysphagia rehabilitation has implications for patients who aren't safe to have any food by mouth as well as those who fatigue easily.

### **2. Background information, description of existing research and information that is already known**

Motor imagery (MI) is the mental rehearsal of physical movement without any body movement and can use various mental frameworks such as auditory, visual, tactile, gustatory, and kinesthetic imagery (Dickstein & Deutsch, 2007). MI has been used in sports science to improve speed, performance accuracy, strength, and movement dynamics of athletes (Taktek, 2004). It has also been used in rehabilitative medicine, specifically physical and occupational therapies, to improve upper and lower extremity function (Peters & Page, 2015). Target patient populations for research have included stroke, spinal cord injury, Parkinson's disease and other neurological disorders. Commonly MI is combined with actual physical practice for optimal rehabilitation outcomes and there is evidence for neural reorganization with MI. MI requires minimal direct supervision, minimal expense and no specialized equipment. Additionally it has no known risk, which is important for patients with high levels of impairment and fatigue.

### **3. The research questions, objectives and purpose**

This is a collaborative project between [name] at USF-Sarasota-Manatee, [name] at James Madison University (JMU), [name] at Loma Linda University (LLU), and [name] at Texas Christian University (TCU). Each study site will acquire IRB approval from each respective university IRB.

This research study is a six-week treatment pilot study to determine the effect of motor imagery for tongue strengthening exercises on measures of tongue strength and swallowing pressure in typically aging older adults. Typically-aging older adults represent a group "at risk" for dysphagia secondary to sarcopenia of striated musculature important to swallowing. Participants

at all study sites will be randomly selected into one of four groups: 1) placebo (active jaw open against resistance/close against resistance/lateralize/protrusion exercises with relaxation exercises), 2) active tongue exercises against resistance only, 3) active tongue exercises against resistance + motor imagery of tongue exercises against resistance, and 4) motor imagery of tongue exercises against resistance only. In some JMU participants we will also determine cortical activation patterns differences during motor execution and motor imagery of tongue exercises between the groups using near-infrared spectroscopy. The results of this study will inform refinement/further development of the mental practice protocol to use with patients with dysphagia in future studies.

The research questions are as follows:

1. Does a 6 week treatment of motor imagery tongue exercises with or without active tongue exercise improve tongue strength in healthy older adults compared to a 6 week treatment of placebo exercises and 6 week treatment of active tongue strengthening exercises?
2. Does a 6 week treatment of motor imagery tongue exercises with or without active tongue exercise improve swallowing pressures in healthy older adults compared to a 6 week treatment of placebo exercises and 6 week treatment of active tongue strengthening exercises?
3. Does a 6 week treatment of motor imagery tongue exercises with or without active tongue exercise alter cortical hemodynamic response patterns in healthy older adults compared to a 6 week treatment of placebo exercises and 6 week treatment of active tongue strengthening exercises? (JMU participants only)

Our hypothesis, based on previous research, is that the group receiving both active and MI treatment will make the most gains in all three measures, followed by the active only group, then the MI only group, then the placebo group (control).

#### **4. The study design including information that is needed to answer the research questions**

Subjects will be recruited by USFSM email blast, word of mouth, and community advertisements (local clubs, community centers, clinics, physician offices).

#### **Compensation Schedule**

- 4 in-person visits for a total of \$60 in Amazon gift cards should a participant complete the entire, 6-week research protocol.
  - Visit 1 (Recruitment Phase 2 & Baseline) - \$20 Amazon gift card provided at end of visit.
  - Visit 2 (end of Week 2 of 6-week exercise program).
  - Visit 3 (end of Week 4 of 6-week exercise program). \$20 Amazon gift card provided at end of visit.
  - Visit 4 (end of Week 6 of 6-week exercise program). \$20 Amazon gift card provided at end of visit.

## **Recruitment (Phases 1 & 2)**

### **Phase 1 Recruitment** (anticipated 20-25 minutes in length):

[figure not shown]
- Telephone pre-screen for verbal consent and inclusion/eligibility telephone screening (includes EAT-10 screening tool) completed with persons responding to advertisement.
  - If preferred by potential subject, a hard copy of the screening forms will be mailed to address provided, including a pre-stamped/labeled return envelope.
  - If preferred by potential subject, an electronic copy of the screening forms will be e-mailed to e-mail address provided and scanned completed screening forms accepted in return.
- Potential subjects meeting the screening forms criteria will be invited for Phase 2 of recruitment + baseline (if eligible) in-person visit at USFSM, participant's home, or private location at a community center (e.g., conference room at an independent living facility) if preferred

### **Phase 2 Recruitment + Baseline (if eligible) (Visit #1)** (Phase 2 Recruitment anticipated 30 minutes in length):

- Each in-person visit will be conducted confidentially and privately at USFSM, a the participant's home, or a private location at a community center.
- Intraoral examination will be completed to confirm absence of tongue piercings/oral apparatus that may interfere with tongue exercises.
- Investigator will administer the Kinesthetic and Visual Imagery Questionnaire (KVIQ-10) and Mini Mental State Examination (MMSE).
- Both the KVIQ-10 and MMSE must be passed to continue.
  - If fails KVIQ-10 or MMSE, the individual will be notified that he/she does not qualify to participate in the study and thanked for taking the time to complete the recruitment activities.
  - If passes both KVIQ-10 and MMSE, detailed study information and informed consent form will be reviewed, with time provided for potential subject to ask questions. Should the potential subject decide to voluntarily participate in the study, informed consent form will be signed and the baseline experimental session will begin.

### **The following equipment will be used to take measures at baseline and other follow up visits:**

1. **Iowa Oral Performance Instrument (IOPI)** - Uses an air filled bulb held in the mouth to measure oral pressures in kilopascals. Maximal isotonic tongue pressures as well as pressures generated from normal swallows will be measured at baseline and three follow up visits (described below). This equipment is portable.

**Baseline Visit #1 Protocol: (anticipated 30 minutes)**

1. Investigator completes basic education and training about how the IOPI is used/protocol for collecting IOPI measurements.			
2. Investigator will measure subject's maximum/peak tongue pressure using IOPI device. 
 
○ Six measurements will be taken, with 30-40 seconds between each.
 
○ Mean value will be used as the subject's maximum tongue strength
 
			
3. Investigator will measure subject's regular swallowing pressures using the IOPI device. Swallows will be completed using the participant's saliva (no water or other liquid given during measurement). 
 
○ Six measurements will be taken, with 30-40 seconds between each.
 
○ Participants will be given 20-30 mL of water to swallow between each rep to help moisten the mouth.
 
○ Mean value will be used as the subject's normal swallowing pressure
 
			
4. Investigator will randomly assign subject to one of four study groups:			
(1) Placebo (control) exercise	(2) Active tongue exercise	(3) Active tongue exercise + Motor Imagery exercise	(4) Motor Imagery exercise
5. Investigator completes jaw exercise training with subject, including basic education about physical strengthening exercise. 
 
○ Instructions will be rehearsed verbally and written instructions will be provided to each subject to use in home environment.
 
○ Limited practice opportunity provided to confirm subject's
 
	5. Investigator completes active tongue exercise training with subject, including basic education about physical strengthening exercise.	5. Investigator completes active tongue exercise training with subject, including basic education about physical strengthening exercise.	5. Investigator completes mental practice exercise training with subject, including basic education about motor imagery and mental practice.


understanding of exercise instructions.
 
 
○ A lightweight, portable counter clicker will be provided to the subject to keep track of active exercise repetitions.
 
 
AND
 
Investigator completes visualization relaxation training with subject.
 
 
○ Instructions will be rehearsed verbally and written instructions will be provided to each subject to use in home environment.*
 
	
 
○ Instructions will be rehearsed verbally and written instructions will be provided to each subject to use in home environment.
 
○ Limited practice opportunity provided to confirm subject's understanding of exercise instructions.
 
○ Tongue depressors will be provided to the subject to use for resistance during active exercises.
 
○ A lightweight, portable counter clicker will be provided to the subject to keep track of active exercise repetitions.
 
	
 
○ Instructions will be rehearsed verbally and written instructions will be provided to each subject to use in home environment.
 
○ Limited practice opportunity provided to confirm subject's understanding of exercise instructions.
 
○ Tongue depressors will be provided to the subject to use for resistance during active exercises.
 
○ A lightweight, portable counter clicker will be provided to the subject to keep track of active exercise repetitions.
 
 
AND
 
Investigator completes mental practice exercise training with subject, including basic education
	
 
○ Instructions will be rehearsed verbally and written instructions will be provided to each subject to use in home environment.
 
○ A lightweight, portable counter clicker will be provided to the subject to keep track of mental practice repetitions (to reduced cognitive load of counting repetitions while completing mental practice). Mental practice instructions are outlined below.**
 
○ Limited practice opportunity provided to confirm subject's understanding of exercise instructions.
 
○ Investigator observes to confirm no overt muscular activity in
 

---	--	--	--

		
about motor imagery and mental practice.
 
 
○ Instructions will be rehearsed verbally and written instructions will be provided to each subject to use in home environment.
 
○ A lightweight, portable counter clicker will be provided to the subject to keep track of mental practice repetitions (to reduced cognitive load of counting repetitions while completing mental practice). Mental practice instructions are outlined below.**
 
○ Limited practice opportunity provided to confirm subject's understanding of exercise instructions.
 
○ Investigator observes to
 
	
head/neck area during motor imagery tasks.

--	--	--	---

		confirm no overt muscular activity in head/neck area during motor imagery tasks.	

6. Investigator instructs subject to complete 1 set (10 repetitions in each direction – open/close/lateralization/protrusion) of placebo exercise, 3x day, 3 days/week for two weeks.
 
AND
 
Following completion of all reps of the active exercises in a given set (10 reps per direction for 40 reps total), subject will find quiet spot (without distraction) to complete relaxation exercises*. This will be repeated 3x/day, 3 days a week for 2 weeks.
	
6. Investigator instructs subject to complete 1 set (10 repetitions) in each direction (protrusion, elevation, left, right), 3x day, 3 days/week for two weeks.
	
6. Investigator instructs subject to complete 1 set of active tongue exercise (10 repetitions) in each direction (protrusion, elevation, left, right). 3x day, 3 days/week for two weeks.
 
AND
 
Following completion of all reps of the active exercises in a given set (10 reps per direction for 40 reps total), subject will find quiet spot (without distraction) to complete mental practice exercises, including 10 repetitions per direction (40 reps) of mental practice tongue exercises. This will be repeated 3x/day, 3 days a week for 2 weeks.
	
6. Investigator instructs subject to complete 1 set of mental practice exercise (10 repetitions) in each direction (protrusion, elevation, left, right), 3x day, 3 days/week for two weeks.


7. A record form will be reviewed and provided to subject, with instructions to document each exercise set complete each week (date and time) and to note any applicable personal comments as warranted (e.g., fatigue, pain, technical difficulty, interruptions during a set). Only the subject's participant number will be recorded on the form.
			

8. An appointment will be scheduled for Visit #2 around two weeks following Visit #1. Attempt to schedule subsequent visits at a consistent time of day, so that max measurements are taken around the same time of
			

day each visit, preferably at the time of day the subject feels strongest.
9. Investigator will process subject's first \$20 participation incentive.

\*Visualization Relaxation Exercise Instructions:

1. Find a comfortable and quiet spot where you will not be distracted.
2. Set a timer for three to five minutes.
3. Choose a place or situation that you find peaceful and calming (e.g., the beach or favorite vacation spot).
4. When ready, start the timer and close your eyes.
5. Imagine yourself in your peaceful and calm place or situation.
6. Try to imagine the smells, sights, sounds, and touch when you are there (e.g., the smell of sunscreen, the sound of water, the sight of children building sand castles, and the feel of the sand between your toes at the beach).
7. Focus on positive thoughts associated with your peaceful and calming place or situation.
8. When your timer rings, open your eyes and count out-loud to 5 to bring yourself back to the present.

Adapted from: Mayo Foundation for Medical Education and Research. (2017). *Stress management: Types of relaxation techniques*. Retrieved from <https://www.mayoclinic.org/healthy-lifestyle/stress-management/in-depth/relaxation-technique/art-20045368?pg=2>

\*\*Mental Practice Exercise Instructions:

1. Set the counter clicker to zero.
2. Assume a comfortable sitting position: seated upright (90°), both feet on the floor, arms resting comfortably in lap, and holding the counter clicker in one hand.
3. Imagine the tongue exercise movements (protrusion, left, right, elevation): use the first-person perspective, as if you were actually executing the exercise.
4. Avoid actually moving or contracting muscles from your tongue, face, head, or neck. Keep a relaxed position.
5. Remember to imagine seeing and feeling the movements from within – imagining completing each repetition as if you are pushing against a tongue depressor.
6. When ready, imagine performing one tongue exercise at a time, using the counter clicker to keep track of each mental exercise repetition completed. Keep breathing normally.
7. If you lose your concentration during a set (10 repetitions in each of the four directions), relax for a few moments and then start the exercise set again, re-setting the counter clicker to zero.
8. Try to make as few errors as possible with each imagined tongue exercise movement.

**Visit #2 (end of Week 2)** (anticipated 30 minutes in length):

1. Investigator will measure subject's maximum/peak tongue pressure using IOPI device.
 
 
○ Six measurements will be taken, with 30-40 seconds between each.
 
○ Mean value will be used as the subject's maximum tongue strength
 
			

2. Investigator will measure subject's regular swallowing pressures using the IOPI device. Swallows will be completed using the participant's saliva (no water or other liquid given during measurement).
 
 
○ Six measurements will be taken, with 30-40 seconds between each.
 
○ Participants will be given 20-30 mL of water to swallow between each rep to help moisten the mouth.
 
○ Mean value will be used as the subject's normal swallowing pressure
 
			

3. Subject's exercise protocol instructions (as indicated) will briefly be reviewed to confirm subject's understanding/correct completion of assigned exercise protocol.
			

(1) No exercise
	
(2) Active tongue exercise
	
(3) Active tongue exercise + Mental practice exercise
	
(4) Mental practice exercise


4. Investigator instructs subject to complete 1 set (10 repetitions in each direction – open/close/lateralization/protrusion) of placebo exercise, 3x day, 3 days/week for two weeks.
	
4. Investigator instructs subject to complete 1 set (10 repetitions) in each direction (protrusion, elevation, left, right), 3x day, 3 days/week for two weeks.
 
 
○ Additional tongue depressors will be provided to subject as needed.
 
	
4. Investigator instructs subject to complete 1 set of active tongue exercise (10 repetitions) in each direction (protrusion, elevation, left, right), 3x day, 3 days/week for two weeks.
 
 
○ Additional tongue depressors will be provided to subject as needed.
 
 
AND
 
Following completion of all reps of the active exercises in a given set (10 reps per direction for 40 reps total), subject will find quiet spot (without distraction)
	
4. Investigator instructs subject to complete 1 set of mental practice exercise (10 repetitions) in each direction (protrusion, elevation, left, right), 3x day, 3 days/week for two weeks.

		to complete mental practice exercises, including 10 repetitions per direction (40 reps) of mental practice tongue exercises. This will be repeated 3x/day, 3 days a week for 2 weeks.	
5. Investigator reminds subject to continue to complete the record form each week.			
6. An appointment will be scheduled for Visit #3 around two weeks following Visit #2. Attempt to schedule subsequent visits at a consistent time of day, so that max measurements are taken around the same time of day each visit, preferably at the time of day the subject feels strongest.			

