It is anticipated that around 40 participants will be recruited to participate in this study across all study sites (around 10 per study group total). As this is a novel pilot study, a power analysis will be conducted using data collected from this investigation when 10 participants have completed the study.

4. Primary Analysis/Results

The investigators hypothesize, based on previous research in the area of motor imagery, that the group receiving both active and MI treatment will make the most gains in all three measures, followed by the active only group, then the MI only group, then the placebo group (control).

Tongue strength means (max and during swallowing) will be analyzed using SPSS in a three way mixed ANOVA. The significance level will be set at $\alpha = .05$.

5. Other Pre-specified Analysis/Results

The investigators will also be looking at cortical hemodynamic response patterns to motor imagery and physical execution of active tongue strengthening exercise between groups with JMU participants only. As this is exploratory in nature, the current investigators are not including a specific hypothesis. Rather, observational/descriptive/proof of concept factors will be explored. If sufficient data is available, a three-way mixed ANOVA will be used to understand effects on percent change in oxygenation during hemodynamic response.

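### The role that assigns and trains participants also takes the maximal-effort pressure readings, with no masking described and no fixed effort prompt, so arm-related coaching could create or hide differences

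*Protocol*

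**What the plan says.** Protocol section 4 lists the steps of each visit and names one role, the investigator, for nearly all of them.

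- **Visit 1.** Baseline pressures are read at steps 2 and 3. Step 4 then says "Investigator will randomly assign subject to one of four study groups". Step 5 is training specific to the arm; for the active tongue arm it reads "Investigator completes active tongue exercise training with subject, including basic education about physical strengthening exercise".
- **Visits 2, 3 and 4.** Step 1 of each visit is "Investigator will measure subject's maximum/peak tongue pressure using IOPI device". Step 2 is the regular saliva-swallow pressure, read by the same role.
- **After the readings.** Visit 2 step 3 is "Subject's exercise protocol instructions (as indicated) will briefly be reviewed to confirm subject's understanding/correct completion of assigned exercise protocol". At Visits 2 and 3 the investigator also gives the exercise instructions for the participant's arm. Visit 4 has no arm-specific step.
- **Standardisation.** "Six measurements will be taken, with 30-40 seconds between each"; "Mean value will be used as the subject's maximum tongue strength" (the swallow readings are averaged in the same way); and, for later visits, "Attempt to schedule subsequent visits at a consistent time of day".

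SAP section 1 makes both pressures primary outcomes. SAP section 4 (and Protocol section 3) states the expected ranking: active plus imagery, then active only, then imagery only, then placebo. The analysis is one sentence: "Tongue strength means (max and during swallowing) will be analyzed using SPSS in a three way mixed ANOVA".

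**The concern.** A maximum-pressure reading depends on how hard the participant presses, and that can depend on what the person holding the device says. If that person knows the arm and expects a ranking, encouragement may differ by arm without any intent.

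Baseline is read before allocation in the listed order, so it should not carry an arm-related shift. Any later shift therefore passes in full into the change from baseline. It would be systematic within an arm, so neither the mean of six readings nor the planned ANOVA can separate it from a treatment effect. Coaching that follows the expected ranking would favour the hypothesis; coaching in the other direction would hide a real effect.

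The consequences could outlast this pilot. SAP section 3 bases a power analysis on its data, and Protocol section 7 foresees their use as pilot data for grant applications.

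**Working it through.** **1. What is fixed and what is open**

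| Element of the reading | Fixed in the plan? |
|---|---|
| Number of readings, rest between them | Yes: six, 30-40 s apart |
| Summary value | Yes: the mean |
| Time of day | Attempted |
| Words used to prompt each effort | No |
| Encouragement during efforts | No |
| Whether readings are disclosed to the participant | No |
| Whether earlier values are visible to the investigator | No |
| Masked or separate assessor | Not mentioned |

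Visit 1 step 1 refers to a protocol for collecting the IOPI measurements but does not give its content. The home imagery and relaxation instructions, by contrast, are written out line by line.

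**2. The plan's own figure**

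SAP section 3: 4 groups x 10 = 40, which agrees with the stated total of around 40. No SD, effect size or power is given, so nothing further can be reproduced.

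**3. Illustration: a false difference**

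Inputs from the documents: n = 10 per arm (SAP section 3) and alpha 0.05 (SAP section 4; taken as two-sided, since this is not stated). Assumed: a coaching shift b between two arms in outcome SDs, a correlation rho of 0.5 to 0.7 between baseline and follow-up, equal SDs, and no true effect.

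- Baseline-adjusted contrast: SE = sqrt(1 - rho²) x sqrt(2/10), with 40 - 4 - 1 = 35 df.
- Change-score contrast: SE = sqrt(2(1 - rho)) x sqrt(2/10), with 40 - 4 = 36 df.
- Rejection probability: two-sided, from the noncentral t distribution with non-centrality b/SE.

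Example: with b = 0.2 and rho = 0.5, the adjusted SE is 0.866 x 0.447 = 0.387, the non-centrality is 0.2/0.387 = 0.516, and the rejection probability is 0.079.

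| Assumed shift b | Adjusted, rho 0.5 / 0.7 | Change score, rho 0.5 / 0.7 |
|---|---|---|
| 0 | 5% / 5% | 5% / 5% |
| 0.1 SD | 5.7% / 6.1% | 5.5% / 5.9% |
| 0.2 SD | 7.9% / 9.3% | 7.2% / 8.7% |
| 0.3 SD | 11.7% / 15.0% | 10.0% / 13.5% |
| 0.5 SD | 24.1% / 33.1% | 19.3% / 29.0% |

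For shifts of 0.2 to 0.3 SD the range is therefore about 7% to 15%. Neither contrast is the planned three-way mixed ANOVA, whose factors are not named.

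**4. Illustration: a hidden difference**

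A plain two-sample t test with 10 per arm (18 df) has 80% power for a true difference of 1.32 SD. An opposite coaching shift of 0.25 SD leaves 1.32 - 0.25 = 1.07 SD and 62% power. A shift of 0.50 SD leaves 0.82 SD and 42%.

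**The case against.** Much can be said for the plan, and several parts of it stand.

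- **Role, not person.** The documents name a role in a four-site study. A reader might infer that one individual assigns, trains and measures each participant while knowing the arm. That is the natural reading, but it is not stated. Knowledge of the arm is inferred from the arm-specific steps and the absence of any masking. At Visit 4 even that cue is weaker, because only the two measurement steps are common to Visits 2 to 4. Part of the protocol, between sections 7 and 9, was not available for review.
- **Partial standardisation.** Number, spacing, averaging and time of day are set, and an effort instruction may exist in the unseen IOPI protocol. This narrows the gap to effort wording, encouragement and feedback. It does not close it, because the reviewed plan binds no site to any wording.
- **The swallow reading.** It is a regular saliva swallow, not a maximal effort. The mechanism applies mainly to maximum tongue pressure.
- **Size and direction.** A reader might infer that the results will be biased toward the hypothesis, or that the true error rate is 15%. The documents support neither: they contain no evidence on the size or direction of any coaching effect, and at 0.1 SD the inflation is negligible. Bias in every contrast along the ranking would also require coaching to follow the full ranking.
- **It is a pilot.** Unmasked assessment is common in small studies and can be reported as a limitation. But most of the remedy needs no second assessor, so limited staffing is no reason to leave the prompt open.

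**Conclusion.** The point holds as a weakness in how the outcome is measured, and it can be improved cheaply. As written, the plan gives allocation, arm-specific training and the follow-up readings to one role with no masking described, states an expected ranking, and leaves effort wording, encouragement and disclosure of readings open. That exposes maximum tongue pressure to a shift that averaging cannot remove, and regular swallow pressure to a lesser one.

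The size is unknown. The 7-15% range rests on an assumed shift of 0.2 to 0.3 SD, an assumed correlation of 0.5 to 0.7, 10 per arm, and contrasts simpler than the planned analysis. It shows that a modest shift would matter; it does not estimate this trial's error rate. No stated figure in the plan is wrong.

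**What to change.** Amend the measurement steps at all four visits and all sites, including baseline before assignment:

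1. Read aloud one fixed instruction for each effort, with the same wording in every arm, and give no other coaching.
2. Do not tell or show readings to the participant until the final visit is over.
3. Keep earlier values out of the investigator's sight while measuring.
4. Record all six readings as taken. Repeat one only for a technical failure defined in advance, and note it on the form.
5. Apply the script from baseline onward for newly enrolled participants, so that conditions do not change between a participant's baseline and follow-up.
6. Optionally, where a site already has a second team member, let that person take the follow-up readings for participants they did not train.
7. State in the report that outcome assessment was not masked.

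The cost is one script and a small change to the paper recording form. Sample size, alpha, visits, equipment and required staff are unchanged. The downsides are that the bias is reduced rather than removed, and that absolute pressures may be slightly lower without encouragement.
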